3.2.2 Dose Rationale

The 300 mg dose of MEDI-551 was selected to achieve complete peripheral B-cell depletion. Based on existing PK and B-cell PD data from Study MI-CP200, a fixed dose of 300 mg MEDI-551 given on Day 1 and Day 15 is predicted to fully deplete peripheral blood B cells to undetectable levels and maintain B-cell suppression for 28 weeks, therefore sustaining B-cell depletion for the duration of the RCP. In theory, an initial dose of MEDI-551 will deplete the peripheral blood B cells; however, additional B cells will then recirculate out of the lymphoid tissues. The second dose of MEDI-551 on Day 15 is timed to deplete the newly recirculated B cells from the peripheral blood.

This dose regimen is supported by clinical data from other B-cell depleting mAbs, where IV dosing on Day 1 and Day 15 will provide optimal B-cell depletion in both blood and tissues ([Huffstutter et al, 2011](#); [Hauser et al, 2008](#); [Bar-Or et al, 2008](#); [Kappos et al, 2011](#)).

A fixed dose of 300 mg MEDI-551 administered on OLP Day 1 (and OLP Day 15 for subjects who received placebo in the RCP) and then every 26 weeks is predicted to fully deplete peripheral blood B cells to undetectable levels and maintain B-cell suppression for the dose interval of the OLP (Figure 2).

Figure 2 PD Model Simulation Supporting Dosing Regimen

PD = pharmacodynamic; Q26W = every 26 weeks

3.2.3 Rationale for Study Population

This clinical study is designed to study the efficacy and safety of MEDI-551 as a maintenance treatment of subjects with established NMO/NMOSD aimed to reduce the risk of NMO/NMOSD attacks. Therefore, the inclusion/exclusion criteria define a group of adult subjects (women and men aged 18 years and above) who must have a diagnosis of NMO/NMOSD at the time of screening and a documented history of 1 or more NMO/NMOSD acute relapses that required rescue therapy within the last year, or 2 or more NMO/NMOSD acute relapses that required rescue therapy within the 2 years prior to screening.

Both AQP4-IgG seropositive and seronegative subjects will be enrolled in the study to fully capture the entire spectrum of this potentially fatal and rare demyelinating neurological disease. There is a series of clinical studies showing that AQP4-IgG is involved in the pathogenesis of NMO and that AQP4-IgG may be predictive of relapse and/or later conversion to definite NMO ([Weinshenker et al, 2006](#); [Matiello et al, 2008](#)). In a multicenter study of 175 Caucasian patients, bilateral ON at onset was more common in AQP4-IgG seronegative patients as was simultaneous ON and myelitis, and the time to diagnosis was shorter in the AQP4-IgG seronegative group. Additionally, the disease course was more often monophasic in AQP4-IgG seronegative patients ([Jarius et al, 2012](#)).

There is strong evidence to support the hypothesis that NMO is a pathologically heterogeneous disease, as even using the most reliable of recombinant assays, there are subsets of subjects who do not test seropositive for AQP4-IgG that may still present with NMO and conditions that may cause myelitis and ON by other mechanisms. It has been speculated that different etiological mechanisms are involved in AQP4-IgG seronegative NMO/NMOSD. Recent studies have identified a subset of AQP4-IgG seronegative NMO patients who are positive for antibodies against myelin-oligodendrocyte glycoprotein (MOG), a protein expressed on the outer surface of the myelin sheath and oligodendrocytes (Kitley, Woodhall et al, 2012; Mader et al, 2011), and for antibodies against CV2/CRMP5 (Jarius et al, 2012). Since an anti-CD19 B-cell depleting mAb will remove the source of AQP4-IgG, it should also remove the source of these antibodies. The clinical presentation of an attack is considered by NMO experts to be indistinguishable between seropositive and seronegative NMO patients.

Several assays have shown to be able to detect AQP4-IgG even in samples taken from subjects during remission and treatment with strong immunosuppressants such as rituximab, AZA, mitoxantrone, and/or cyclophosphamide, plausibly ruling out the likelihood that seronegativity is generally the result of insufficient assay sensitivity.

In addition, evidence for the therapeutic effect of B-cell depletion with rituximab in NMO seropositive and seronegative subjects is supported by a number of uncontrolled studies comparing relapse rates and EDSS scores before and after treatment (Jacob et al, 2008; Bedi et al, 2011; Kim SH et al, 2011; Ip et al, 2013).

The AQP4-IgG status was available in all subjects in the previously described rituximab studies, with seronegative status occurring in nearly 20% to 30% of NMO/NMOSD patients tested.

Thus, this study population will include approximately 80% subjects who are AQP4-IgG seropositive and 20% of subjects who are AQP4-IgG seronegative. In subjects who are AQP4-IgG seronegative, the diagnosis of NMO is less clear; therefore, these subjects must meet the clinical criteria for NMO according to Wingerchuk et al, 2006 and not have brain MRI lesions consistent with MS. In addition, screening data of these subjects will be reviewed by an independent Eligibility Committee to confirm the diagnosis of NMO in the absence of AQP4-IgG seropositive status.

The study allows for inclusion of a wide age range of subjects as recent international research has shown under-representation of older participants in clinical studies. It is both unhelpful for optimal healthcare as well as fundamentally unjust to exclude participants from clinical research based solely on an arbitrary age limit (Briggs et al, 2012).

3.2.4 Rationale for Endpoints

3.2.4.1 Primary Endpoint

The primary endpoint of time (days) from Day 1 to onset of an AC-determined NMO/NMOSD attack on or before Day 197 is based on the natural history of the disease, which is characterized by a stepwise deterioration of motor, sensory, visual, and bowel/bladder function (Sellner et al, 2010), and recurrent attacks that can result in blindness, paralysis, and even death. Attacks of NMO/NMOSD are more severe than MS and usually result in incomplete recovery and permanent deficits. Thus, establishing a primary endpoint using an annualized relapse rate as usually utilized in MS studies where subjects typically have mild attacks and exacerbations followed by varying degrees of recovery, would expose subjects to a longer study period with an increased risk to the placebo subjects. Utilizing time to attack as the primary endpoint limits subject exposure but still provides a robust endpoint.

3.2.4.2 Secondary Endpoints

Worsening from Baseline in EDSS at Last Visit During the Randomized-controlled Period

A subject will be considered to have a worsening in overall EDSS score if one of the following criteria is met:

- (a) Worsening of 2 or more points in EDSS score for patients with baseline score of 0.
- (b) Worsening of 1 or more points in EDSS score for patients with baseline score of 1 to 5.
- (c) Worsening of 0.5 points or more in EDSS score for patients with baseline score of 5.5 or more.

Myelitis attacks in NMO/NMOSD patients are severe and may lead to permanent disability. Measurement of disease progression in NMO/NMOSD patients is critically important since the potential for recovery depends on the severity of the attacks. The EDSS is a commonly used measure of disability in MS, and given the lack of any validated scales for NMO, is widely considered appropriate for measuring the level of disability in patients with NMO/NMOSD. Because the time to achieve these EDSS scores is often long, a short-term indicator of disease progression can be applied to the disease course by using an increase in EDSS score sustained over several months called “sustained disease progression.” Several definitions of sustained disease progression for clinical trials and observational studies have been proposed, including a 2- or more point increase in EDSS score for patients with a baseline score of 0; an increase in 1 point or more in EDSS score for patients with a baseline score of 1-5; or an increase of 0.5 points or more in EDSS score for patients with a baseline score of 5.5 or more has been used in the literature.

Change from Baseline in Low-contrast Visual Acuity Score, Measured by Low-contrast Landolt C Broken Rings Chart at Last Visit During the Randomized-controlled Period

Visual loss and dysfunction are recognized disabling clinical manifestations in patients with NMO/NMOSD. In MS clinical trials, low-contrast visual acuity emerged as the leading candidate to measure visual disability in MS. Subsequent studies found that low contrast acuity testing correlated well with brain MRI lesion burden, visual evoked potentials and retinal nerve fiber layer (RNFL) loss as measured by optical coherence tomography (OCT). Worsening of visual function by a clinically significant > 7 letters or approximately 1.5 lines for low-contrast acuity is associated with approximately 4.5 μm reduction in RNFL thickness in MS. Additional longitudinal studies have shown RNFL axonal loss over time that occurs even in the absence of an acute ON attack and correlates with clinical meaningful worsening of vision and quality of life in patients with MS. The low-contrast visual acuity test is used to determine the number of letters that can be read on a standardized low-contrast Landolt C Broken Rings Chart held at a distance of 3 meters. Due to lack of standard visual function measures specific to NMO/NMOSD, and the fact that both MS and NMO/NMOSD patients can experience ON, and this endpoint has been previously used widely in MS studies, there is good rationale for using this endpoint in this NMO/NMOSD study. This secondary endpoint will evaluate whether MEDI-551 will have an effect on improving vision sensitivity.

Reduction in the Cumulative Total Active MRI Lesions (New Gd-enhancing or New/Enlarging T2)

In clinical practice there is wide use of MRI in the diagnosis and management of NMO; however, the role of MRI in this setting is not well established and studied. The actual interpretation of MRI related to the diagnosis and the follow up of patients with NMO/NMOSD are not consistently established. Therefore, this study aims to collect longitudinal MRI data during both study periods including at the time of an attack, to investigate the characteristics and evolution of spinal and brain lesions in NMO/NMOSD.

Number of NMO/NMOSD-related In-patient Hospitalizations During the Randomized-controlled Period

Patients with relapsing NMO/NMOSD have recurrent attacks that can be severe and result in blindness, paralysis, and even death (Oh and Levy, 2012). Consequently, such attacks frequently result in in-patient hospitalizations. Less severe attacks can be managed without the need for hospitalization. Post initial acute phase of an attack, the patient will often require ongoing care and rehabilitation in the recovery phase post an attack. Therefore, this secondary endpoint will evaluate whether MEDI-551 will be effective in reducing NMO/NMOSD-related hospitalizations compared to placebo. All hospitalizations recorded during the RCP will be included in the analysis.

In-patient hospitalization, for the purposes of analysis of the secondary endpoint, is defined as a stay in hospital that goes beyond midnight of the first day of admission. Any duration of stay

(calculated as the difference between discharge date and admission date) of more than 1 day will contribute to this endpoint. This includes the time a subject may enter an emergency department plus subsequent admission to a ward. Hospitalizations for the administration of NMO-related medications or procedures only (ie, the administration or procedure was isolated and not provided during a subject's hospitalization due to NMO for another reason) will not be included in the secondary endpoint analysis.

Annualized Attack Rate (Total Number of Adjudication Committee-determined NMO/NMOSD Attacks Normalized by Total Person-years) During any Exposure to MEDI-551

This endpoint will be evaluated in all subjects who receive at least one dose of MEDI-551.

This secondary endpoint will be an important marker for assessing frequency of AC-determined NMO/NMOSD attacks during long-term treatment with MEDI-551. Although no comparator is available for long-term comparison, a descriptive summary of AC-determined NMO/NMOSD attack rate over various lengths of exposure to MEDI-551 will provide a sense of constancy of attack rate.

Safety and Tolerability of MEDI-551

The safety and tolerability endpoints are designed to evaluate the safety and tolerability of administration of MEDI-551 in subjects with NMO/NMOSD for this study population. These endpoints will be assessed primarily by summarizing TEAEs and TESAEs, and changes from baseline in laboratory measurements (including ADA status and titers and vaccine titers [see below]), significant physical examination findings, and vital sign measurements.

Vaccine Titers

Vaccination results in immunological memory by expansion of antigen specific CD4+ T-helper and CD8- cytotoxic cells as well as through induction of antigen-specific B-cell cell maturation and antibody secretion (Siegrist, 2013). Given the depletion effect of MEDI-551 on B cells, it is mechanistically relevant to investigate whether immunization responses are diminished by following vaccine-generated antibody titers, including tetanus.

3.2.4.3 Exploratory Endpoints

Change from Baseline in the Short Form-36 Physical and Mental Component Scores (4-week Recall Version)

The literature provides evidence of the strong impact NMO has on HRQoL (Chanson et al, 2011; Kanamori et al, 2011). In one study, the main impact was on PCS (Chanson et al, 2011); however, both PCS and MCS scores on the SF-36 Health Survey were significantly lower in NMO than for the general population, even in the cohort of patients outside an NMO attack period and with relatively low EDSS (mean score: 3.5), indicating the importance of the HRQoL evaluation in NMO.

Change from Baseline in Pain Numeric Rating Scale

A number of recent publications have indicated that patients with NMO/NMOSD experience pain throughout the course of their disease. Pain in demyelinating and inflammatory CNS diseases can be disabling and may contribute to a lower quality of life and overall increased health care burden. Neuromyelitis optica is associated with extensive spinal cord injury, brainstem disorders, ON, and sometimes a combination of these (Qian et al, 2012) and pain in five different locations (eyes, legs, arms, upper back and lower back, respectively) will be measured at baseline and monthly thereafter throughout the study.

B-cell Counts (Total and Subsets)

As MEDI-551 binds to and depletes CD19+ B cells, the depletion is a direct measure of PD effect. Additionally, CD19+ plasmablasts are increased in the peripheral blood on NMO/NMOSD patients and produce anti-AQP4 antibodies. Since AQP4-IgG titers correlate with disease activity (Jarius et al, 2008; Kim et al, Sept 2011), the extent and/or duration of B-cell/plasma-cell depletion may correlate with response to MEDI-551 in these subjects.

Plasma Cell Gene Signature

Production of pathogenic autoantibodies by plasma cells is a hallmark of autoimmune diseases; thus, plasma cell levels may be associated with the efficacy of B-cell depleting therapies like MEDI-551. Flow cytometry methods commonly used to enumerate and describe plasma cells are difficult to implement routinely in large clinical studies because of the insufficient stability of plasma cells. For this reason, whole genome microarray analysis of sorted cellular fractions was used to develop a highly sensitive and specific gene expression signature comprised of multiple plasma cell-enriched genes. In Study MI-CP200, MEDI-551 caused a statistically significant, dose-dependent depletion of the plasma cell gene signature. Thus, it would be relevant to characterize the effect of MEDI-551 on plasma gene signature in patients with NMO/NMOSD.

Subpopulations of CD19+ and CD20- B cells showing properties of plasmablasts are increased selectively in the peripheral blood of NMO/NMOSD patients and anti-AQP4 antibodies are produced by these cells. These B-cell subsets have been shown to expand 2 weeks prior to and during NMO/NMOSD attacks. Measuring the depletion of plasma cells/plasmablasts will provide key PD information as MEDI-551 should deplete this cell population. The levels of the plasma cell signature prior to and following MEDI-551 treatment may provide information about which patients are more likely to respond to this therapy and/or predict an attack.

Serum AQP4-IgG Titers

Several previous studies determined that AQP4 antibody levels correlated with clinical disease activity, with relapses associated with up to a 3-fold increase in AQP4 antibody titers (Jarius

[et al, 2008](#)). Since CD19+ plasmablasts produce pathogenic anti-AQP4 antibodies, it will be important to characterize the time course and extent of the effect of MEDI-551 on AQP4-IgG titers.

3.2.4.4 Exploratory Investigations

Levels of Soluble and Genomic Biomarkers (eg, Cytokines, Chemokines, Immunoglobulins, and mRNA/Micro-RNA), and Relevant Cell Counts

A number of biomarkers that may provide additional insights into the mechanism of action of MEDI-551 in NMO/NMOSD or potentially predict response to MEDI-551 will be explored. An example of a relevant biomarker is BAFF, which is a cytokine that acts as a potent activator of B cells and plays an important role in the proliferation and differentiation of B cells. As the primary receptor for BAFF is expressed on mature B cells, it has been demonstrated that circulating BAFF is inversely correlated with B-cell depletion. Other serum biomarkers such as CCL19 and CXCL13 are also related to B-cell dynamics and may predict responses to B-cell depleting therapies.

T-cell Responses

There is increasing evidence for the involvement of effector T cells in the pathogenesis of NMO (reviewed in [Mitsdoerffer et al, 2013](#)). AQP4-specific antibodies in NMO serum are immunoglobulin G1 (IgG1), a subclass of mature IgG that requires help from T cells. T cells from NMO patients demonstrated greater proliferation to AQP4 and AQP4 peptide fragments than those from healthy controls ([Varrin-Doyer et al, 2012](#)). Therefore, antigen-specific T cells may contribute to the generation of AQP4-IgG in the peripheral immune compartment and to the development of NMO lesions in the CNS.

B-cell depletion, both *ex vivo* and *in vivo*, resulted in diminished proliferative and proinflammatory cytokine responses of both CD4 and CD8 T cells of MS patients ([Bar-Or et al, 2010](#)). It is mechanistically relevant to investigate whether T-cell responses are also diminished following B-cell depletion in NMO patients.

4 MATERIALS AND METHODS

4.1 Subjects

4.1.1 Number of Subjects

A maximum of 252 subjects will be randomized and dosed in this study. Because this study is event-driven where the primary objective is based on a total of 67 AC-determined NMO/NMOSD attacks, and the rate of NMO/NMOSD attacks is not established in the literature, this number of subjects was determined by analyzing masked data of the actual attack rate from the first 78 subjects who completed the RCP in this study. The attack status (attack/no attack) of the 78 subjects was randomly sampled with different attack rate, which gave an estimate of the number of attacks for the total sample size. This simulation process

was repeated 10,000 times to give a distribution of the number of attacks for the total sample size, from which the probability of observing at least 67 attacks could be estimated. Based on the 78 completed subjects, this procedure showed that with 252 subjects there is a 90% probability of reaching the required 67 AC-determined attacks.

Of the total number of subjects enrolled, approximately 80% will be AQP4-IgG seropositive and 20% will be AQP4-IgG seronegative.

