6.3 Study Timetable and End of Study

The end of the study ("study completion") is defined as the date of the last protocol-specified visit/assessment (including telephone contact) for the last subject in the study. This will occur when the last subject completes the 52-week SFP.

An individual subject will be considered to have completed the RCP if the subject was followed through Day 197 or experienced an NMO/NMOSD attack as determined by the AC, regardless of the number of doses the subject received. Additionally, all subjects enrolled in the RCP at time that the 67th AC-determined attack is confirmed, or at the time the Sponsor discontinues enrollment upon recommendation of the independent DMC based on evidence of efficacy and safety, will also be considered as completers, regardless of the number of doses the subject received, provided the subject completes the Day 197/EDV visit. A subject will be considered to have completed the OLP if the subject participated for the duration of the OLP as per Section 3.1.1.4. A subject will be considered to have completed the SFP if the subject was followed for 52 weeks (12 months) after the last dose of investigational product. Subjects will be considered not to have completed a study period if consent was withdrawn, death occurred, or the subject was lost to follow up.

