As the rate of NMO/NMOSD attacks is not established in the literature, a masked sample size reassessment when 50% of the 212 planned subjects completed the RCP was originally part of the protocol. This reassessment was important to protect against the loss of statistical power in the seropositive cohort as well as the ITT population due to not achieving the required number of events. However, the masked interim sample size reassessment was removed from the protocol as a result of a discussion with the FDA regarding the timing of the sample size reassessment as related to the futility analysis. As the study progresses it becomes possible that the futility analysis will occur prior to the sample size reassessment, which would not allow the sample size reassessment to be performed. Therefore, an agreement was reached with the FDA that the sample size reassessment would be removed from the protocol. Instead the study, which is event driven, will continue to enroll until 67 AC-determined NMOSD attacks have occurred, or until a maximum of 252 patients have been randomized (whichever occurs first).

[figure not shown]
The maximum number of 252 randomized subjects was determined by analyzing the actual attack rate based on masked data from the first 78 subjects who completed the RCP in this study. The attack status (attack/no attack) of the 78 subjects was randomly sampled with different attack rate which gave an estimate of the number of attacks for the total sample size. This simulation process was repeated 10, 000 times to give a distribution of the number of attacks for the total sample size, from which the probability of observing at least 67 attacks could be estimated. Based on the 78 completed subjects, this procedure showed that with a

sample size of 227 there is a 50% probability of reaching the required 67 AC-determined attacks and with 252 subjects there is a 90% probability of reaching the required 67 AC-determined attacks. The sample size of 252 subjects was selected to give a high degree of confidence that 67 attacks will be observed in this study.

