Appendix 1 Sample Size Calculation

The proposed study is being planned to detect a target relative reduction of 60% in risk for time (days) from Day 1 to onset of an AC-determined NMO/NMOSD attack on or before Day 197 with 90% power and $\alpha = 0.05$ (two-sided), assuming an unequal randomization ratio of 3:1 to MEDI-551 versus placebo. Using the following formula, a total of 67 AC-determined NMO/NMOSD attacks will be required:

$$E = \left[\frac{z_{1-\alpha/2} + z_{1-\beta}}{\ln(HR)} \right]^2 \times \frac{(r+1)^2}{r},$$

where $z_{1-\alpha/2}$ and $z_{1-\beta}$ are $100(1 - \alpha/2)^{\text{th}}$ and $100(1 - \beta)^{\text{th}}$ percentile of a standard normal distribution, $r = 3$ is the randomization ratio and $HR = \text{hazard ratio} = 0.4$.

Following the completion of the first 78 subjects in this study the sample size was reviewed. The attack rate of the first 78 subjects to complete the RCP was used to simulate the remaining subjects to estimate the probability of reaching the required 67 AC-determined attacks. The simulation showed that with a sample size of 252 subjects there is a 90% probability of reaching the required 67 AC-determined attacks.

The remaining text in this appendix describes the process of defining the original sample size of 212 subjects.

Assuming hazard rates of 1.5/year and 1.0/year for an NMO/NMOSD attack in the placebo arm for seropositive and seronegative groups, respectively, and using the following formula:

$$N = \frac{E}{\Pr(\text{Fail})},$$

a total of 212 (with an upward adjustment) subjects are expected to be enrolled in this study where

$$\Pr(\text{Fail}) = s_1 P_1 + s_2 P_2$$

is the weighted average of the failure probabilities P_1 and P_2 in seropositive and seronegative cohorts, respectively, with associated stratum specific weights $s_1 = 0.8$ and $s_2 = 0.2$. Recall that subjects will be enrolled to seropositive and seronegative cohorts in 80:20 ratio.

Furthermore, the probability of an attack within i^{th} cohort ($i = 1, 2$) is given by

$$P_i = (1 - w)p_{i0} + wp_{i1}$$

the weighted average of the failure probabilities p_{i0} and p_{i1} for placebo and MEDI-551 groups, respectively; $p_{i0} = 1 - e^{-\lambda_{i0}F}$, $p_{i1} = 1 - e^{-\lambda_{i1}F}$; $F = 197/365 = 0.54$ to indicate the 197 days (28 weeks) duration of the controlled portion of the study; note that based on the

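### The 90% chance of 67 attacks at 252 subjects rests on an attack rate that is biased upward as its source is described, because an attack itself counts as completing the RCP

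*Protocol*

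**What the plan says.** Protocol 4.1.1 and 4.8.2 base the maximum of 252 on the "actual attack rate from the first 78 subjects who completed the RCP in this study" and describe the simulation thus: "The attack status (attack/no attack) of the 78 subjects was randomly sampled with different attack rate". The result is that "with 252 subjects there is a 90% probability of reaching the required 67 AC-determined attacks". Appendix 9 adds a second point on the same curve: "sample size of 227 there is a 50% probability of reaching the required 67 AC-determined" attacks. SAP Appendix 1 says how the rate was carried forward: "The attack rate of the first 78 subjects to complete the RCP was used to simulate the remaining subjects". The synopsis puts the probability above 90%; 4.1.1, 4.8.2, Appendix 9 and SAP 2.4 put it at 90%.

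Protocol 6.3 defines who completes the RCP. A subject has "completed the RCP if the subject was followed through Day 197 or experienced an NMO/NMOSD attack as determined by the AC". Subjects are considered "not to have completed a study period if consent was withdrawn, death occurred, or the subject was lost to follow up".

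Neither document gives the number of attacks among the 78, the date of the data cut or the accrual pattern. Neither says that the 78 were limited to subjects randomized at least 197 days before the cut, that a time-to-event estimate was used, or that subjects still in the RCP were counted.

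**The concern.** Under 6.3 a subject who attacks in week 6 is a completer soon afterwards. A subject who does not attack becomes one only at about Day 197. If the first 78 completers are taken while enrolment is running, the set includes recent entrants who attacked and leaves out recent entrants who are still attack-free. The attack proportion in that set exceeds the 197-day risk in expectation. This is selection on outcome, not sampling error, and a larger set would not by itself remove it.

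Resampling attack/no-attack status inherits the bias. Power rests on 67 attacks, and Appendix 9 presents 252 as giving high confidence of reaching them, in place of a sample size reassessment that had been meant to protect power. If the rate is too high, the risk of a shortfall is understated.

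**Working it through.** **1. Required events.** Formula in Protocol Appendix 9 with HR 0.4, two-sided alpha 0.05, 90% power and 3:1 allocation: (1.960 + 1.282)² / (ln 0.4)² × 16/3 = 66.7, so 67. This agrees with the plan.

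**2. The stated 90% and 50%.** Let x be the attacks among the 78. Keep x and draw the other N − 78 subjects at rate x/78, as the SAP describes; the probability is P(Binomial(N − 78, x/78) ≥ 67 − x).

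| x of 78 | Rate | N = 227 | N = 252 |
|---|---|---|---|
| 22 | 28.2% | 32.2% | 77.8% |
| 23 | 29.5% | 52.6% | 90.4% |
| 24 | 30.8% | 72.1% | 96.7% |

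Only x = 23 fits both stated figures. It is an inference, since the documents do not give x.

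**3. Size of the bias.** Assumptions: uniform accrual, 78th completion T days after first entry, and the planning hazards of Appendix 9 (1.5, 0.6, 1.0 and 0.4 per year, weights 0.20, 0.60, 0.05 and 0.15) scaled by a common factor k. Let F(u) be the resulting attack probability by day u, p = F(197), and A the integral of F(u) from 0 to 197. Then

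share of attackers among completers = [(T − 197)p + A] / [(T − 197) + A].

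Solve for k so that the share is 67/227 = 29.5%. For T = 550: k = 0.698, p = 0.2443, A = 25.46, and (353 × 0.2443 + 25.46) / (353 + 25.46) = 111.70/378.46 = 29.5%.

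**4. Chance of 67 attacks at 252.** For T = 550, the number randomized by the cut is 78 × 550/378.46 = 113. So 35 are still in the RCP, with residual risk (550 × 0.2443 − 111.70) / (550 − 378.46) = 13.2%, and 139 are still to enter at 24.4%. Expected attacks: 23 + 35 × 0.132 + 139 × 0.244 = about 61.6. Summing the two binomials gives P(at least 67) = 18%.

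| T (days) | True 197-day rate | Randomized by cut | P(≥ 67 at 252) | Expected attacks at 252 |
|---|---|---|---|---|
| 550 | 24.4% | 113 | 18% | 61.6 |
| 700 | 25.7% | 103 | 38% | 64.9 |
| 850 | 26.5% | 97 | 52% | 66.8 |
| 960 | 26.9% | 95 | 59% | 67.7 |
| 1100 | 27.3% | 92 | 65% | 68.7 |

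(Expected attacks ignore the stop at 67.) On T: the original protocol is dated 13 January 2014 and the SAP amendment history records the increase to 252 on 27 February 2017, which is 1,141 days later.

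**5. Fuller model.** Allow 14 days for adjudication and, as an extreme, no attacks through Day 21 while protocol steroids run. F(u) becomes F(u − 21), the attackers counted become (T − 14 − 197)p + A, and non-attackers stay at (T − 197)(1 − p). The true rate is then 25.5% at T = 550 and 27.8% at T = 1100, and the chance of 67 is about 33% and 72%.

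**6. Check by simulation.** Simulated staggered entry at the unscaled planning hazards (true rate 32.7%) gives an average of 34.6% among the first 78 completers at 2 subjects a month and 40.5% at 8 a month. Subjects randomized at least 197 days before the same cut average 32.3%, so that cohort has no upward bias.

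**7. Power.** Φ(|ln 0.4| × √(3E/16) − 1.960), with the seropositive cohort having 80% of attacks:

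| Attacks E | ITT | Seropositive (0.8E) |
|---|---|---|
| 67 | 90.1% | 82.8% |
| 64 | 88.8% | 81.0% |
| 62 | 87.8% | 79.8% |
| 58 | 85.6% | 77.1% |

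**The case against.** - **The consequence is overtaken.** Amendment 6 implements the decision to stop enrolment on the DMC's recommendation, and the primary data cutoff now has a trigger for that. A reader might infer that the trial will run to 252 and fall short of 67. The documents do not support that, because 252 need not be what ends accrual. This stands: the point corrects a justification that remains in the current documents.
- **The power loss is small.** A fall from 90% to 18% in the chance of 67 sounds severe, but missing 67 by a few attacks costs about 1 to 4 points of ITT power. This stands, and it limits the weight of the point.
- **The size cannot be recovered.** The 23 is back-solved and accrual is unknown. The phrase about a different attack rate may mean the rate was varied, which would weaken the inference. This stands for the size. It does not rescue the direction, since varying the rate around a biased centre leaves the centre biased.
- **A constant hazard from Day 1 with instant adjudication overstates the bias.** This is correct; step 5 shows that the bias shrinks but remains.
- **The 78 may have been a matured cohort.** If all were at least 197 days past randomization, this bias disappears. The text describes them only by completion and states no such restriction.

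**Conclusion.** As the method is described, the 90% is not supported. Under staggered entry, a rate taken from the first subjects to complete, with attack counting as completion, overstates the 197-day risk. That direction follows from 4.1.1 and 6.3 together, on the condition that the 78 were not a fully matured cohort.

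The size is a range and rests on 23 of 78 attacks, uniform accrual and the shape of the planning hazards. The true rate is about 24-28% instead of 29.5%, and the chance of 67 attacks at 252 is about 18-65%, or about 33-72% with adjudication lag and the steroid period. No single value in these ranges should be quoted as the true probability. Leaving withdrawn, dead and lost subjects out of the 78 may also shift the rate; that is not quantified here.

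Power would be about 86-89% in the ITT population and 77-81% in the seropositive cohort at 58-64 attacks, against about 90% and 83% at 67 (the protocol says approximately 82% for the latter). A reader might go further and infer a biased treatment comparison or an inflated type I error. Neither follows: the rate is pooled and masked, and it sets only a cap on enrolment.

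**What to change.** 1. State how the 78 were selected: the date of the cut, and whether first means by exit or by randomization order. If all were at least 197 days past randomization, one sentence saying so settles the point.
2. Otherwise, re-estimate the masked 197-day attack risk by pooled Kaplan-Meier over all subjects randomized and dosed by that cut, or use only those randomized at least 197 days before it.
3. Rerun the simulation with that rate, applying the residual risk to subjects then still in the RCP. Restate the probability of 67 attacks, with the expected number of attacks and the power at 252, in the protocol synopsis, 4.1.1, 4.8.2 and Appendix 9, and in SAP 2.4 and Appendix 1. Bring the synopsis figure (above 90%) into line with the others at the same time.

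The cost is one masked re-analysis of data already collected and, probably, a less favourable stated probability. Enrolment, the analysis model and the alpha allocation do not change.
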